1.3 Number of Patients

The primary endpoint of the study is PFS. Approximately 145 patients will be randomised (3:2 ratio of olaparib:placebo) and the final PFS analysis will occur once approximately 87 PFS events (confirmed via a central review, DCO1) have occurred. A single interim PFS analysis for futility will be performed when 50% of the PFS events required for the final analysis (approximately 44 PFS events) based on BICR have occurred.

The study is sized assuming a true treatment effect that is a PFS hazard ratio (HR) of 0.54 at the final analysis, assuming 80% power and 2.5% alpha (1-sided), with 3:2 randomisation (olaparib:placebo). Assuming PFS is exponentially distributed, a PFS HR of 0.54 equates to a 3.4 month improvement in median PFS over an assumed 4 month median PFS for placebo.

Patients are to be followed for the final analysis of OS and PFS2 (when approximately 106 death events have occurred, DCO2). With 106 OS events the study has 80% power to show a statistically significant difference in OS at the 1-sided 2.5% level if the assumed true treatment effect is a HR 0.57; this translates to an approximate 6-month improvement in median OS over an assumed 8 month median OS on placebo, assuming OS is exponentially distributed.

Assuming that the study accrual period will be approximately 15 months, 87 PFS events are anticipated to be observed approximately 18 to 19 months after the first patient is randomised in the study. It is estimated that 44 PFS events will occur approximately 13 to 14 months after first patient in. It is estimated that 106 deaths will have occurred approximately 31 months after first patient in.

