4.2 Analysis Methods

A single interim PFS analysis for futility will be performed when 50% of the final number of progression events has been reached (approximately 44 PFS events). A final PFS analysis will be performed when approximately 87 progression events have occurred (60% maturity) (DCO1). No further analyses of PFS are planned beyond this point.

One interim analysis for OS will be performed at the time of the final PFS analysis (approximately 87 PFS events). A final formal analysis of OS will be performed when approximate 106 death events have occurred (DCO2). **CCI**

Individual efficacy response data will be listed in a by-patient listing.

A summary of the outcome variables to be analysed at each DCO is shown in [Table 10](#) below.

Table 10 **Timing of Statistical Analyses**

Timing of analysis	Outcome Variable
Interim PFS when ~44 PFS events reported	PFS
Final PFS when ~87 PFS events reported (DCO1)	PFS, PFS2, TDT, TFST, TSST, OS, ORR, BoR, DoR and adjusted mean change from baseline in global HRQoL score.
Final formal OS when ~106 OS events reported (DCO2)	OS, PFS (investigator assessment), PFS2, TDT, TFST, TSST, and adjusted mean change from baseline in global HRQoL score.
CCI	

Safety variables will be analysed at each analysis time point.

There will be no further analyses done unless requested by health authorities.

The treatment comparison is olaparib 300 mg bid versus placebo.

The following table details which efficacy endpoints are to be subject to formal statistical analysis, together with pre-planned sensitivity analyses making clear which analysis is regarded as primary for that endpoint.

Table 11 **Formal Statistical Analyses to be Conducted and Pre-Planned Sensitivity Analyses**

Endpoints Analysed	Notes
PFS	Primary analysis: log-rank test using BICR data
	Key sensitivity analyses: log-rank test using BICR data in randomised patients confirmed as gBRCA mutation positive by the Myriad test (if subset of FAS)
	Additional sensitivity analyses:
	1) Evaluation time bias analysis; log-rank test using BICR data
	2) Attrition bias analysis (using alternative censoring rules); log-rank test using BICR data
	3) Ascertainment bias analysis; log-rank test using investigator data

Table 11 Formal Statistical Analyses to be Conducted and Pre-Planned Sensitivity Analyses

Endpoints Analysed	Notes
	4) Deviation bias analysis (if meaningful to do); log-rank test using BICR data
OS	Primary analysis: log-rank test

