4.2.2.2 Progression-free survival subgroup analyses

Subgroup analyses will be conducted comparing PFS between treatments. The purpose of the subgroup analyses is to assess the consistency of treatment effect across potential or expected prognostic factors. KM plots will be produced for each subgroup according to treatment group.

If there are too few events available for a meaningful analysis of a particular subgroup (it is not considered appropriate to present analyses where there are less than 5 events in a subgroup in at least one treatment group), the results of the subgroup analysis (HR and 95% CI) will not be presented, however, all patients with non-missing subgroup data will be included in the Cox model used for the analysis (see below).

The following subgroups will be analysed for PFS:

- Previous chemotherapy (FOLFORINOX variants, gemcitabine/cisplatin, other); Reference=FOLFORINOX variants
- Type of previous chemotherapy (doublets, triplets, other); Reference=doublets
- Time on first-line treatment till randomisation (≤ 6 months vs > 6 months); Reference= ≤ 6 months
- Best response on first-line treatment (SD vs PR/CR); Reference=SD

These will be determined from the "Metastatic Pancreas Cancer Therapy" (CAPRX2) module of the eCRF at screening by medical review.

- Presence or absence of biliary stent; Reference=Presence of biliary stent

This will be determined from the "Surgical History" (HISS) module of the eCRF at screening by medical review.

- Measurable versus non measurable disease / NED at baseline; Reference=non measurable disease / NED at baseline

This will be determined programmatically from the baseline BICR results.

- gBRCA mutation type (BRCA1, BRCA2, BRCA1/2 (both), non-gBRCAm); Reference=BRCA1

This will be determined programmatically from the Myriad central laboratory test results.

- Age at randomisation (≥ 65 vs < 65); Reference= < 65
- Race (White vs Other); Reference=White
- Sex (Male vs Female); Reference=Male

These will be determined programmatically from the “Demography” (DEM) module of the eCRF at screening.

- ECOG performance status (normal activity, restricted activity); Reference=normal activity

The data will be determined from the “ECOG Performance Status” (PSTAT) module of the eCRF at screening.

Other baseline variables may also be assessed if there is clinical justification. A final decision will be made at the BDRM.

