If the global interaction test is found to be statistically significant, an attempt to determine the cause and type of interaction will be made. Stepwise backwards selection will be performed on the saturated model, whereby (using a 10% level throughout) the least significant interaction terms are removed one-by-one and any newly significant interactions re-included until a final model is reached where all included interactions are significant and all excluded interactions are non-significant. Throughout this process all main effects will be included in the model regardless of whether the corresponding interaction term is still present. This approach will identify the factors that independently alter the treatment effect and prevent identification of multiple correlated interactions.

Any quantitative interactions identified using this procedure will then be tested to rule out any qualitative interaction using the approach of [Gail and Simon 1985](#).

For all subgroups, median PFS time and 95% confidence intervals calculated using the Kaplan Meier method will be summarised by treatment group.

In order to assess the impact of imbalances between treatment groups in terms of the key prognostic variables best response on first-line treatment (CR/PR, SD), time on first-line treatment (≤ 6 months, > 6 months), age group (< 65 years, ≥ 65 years), ECOG status at baseline (0 normal activity, 1 restricted activity), and previous chemotherapy (FOLFORINOX variants, Gemcitabine/Cisplatin, Other), a Cox proportional hazards model including only treatment group will be compared with a Cox proportional hazards model including treatment group and key prognostic variables. The hazard ratio for treatment group and 95% confidence intervals will be presented.

A by-patient listing will be produced for presenting individual PFS data.

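### The SAP guarantees that 10% backward selection of PFS interactions will identify independent effect modifiers and prevent correlated ones; it guarantees neither, and when it is run it usually also names a spurious factor

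*SAP*

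**What the plan says.** SAP section 4.2.2.2 lists eleven baseline factors for PFS subgroup analysis and leaves room for more. Two of them overlap by construction: previous chemotherapy regimen, and "Type of previous chemotherapy (doublets, triplets, other); Reference=doublets". Each factor has its own Cox model with treatment, factor and their interaction, which feeds the forest plot.

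A global test then compares a Cox model holding all covariates and interactions with one that omits the interactions, at a two-sided 10% level. A covariate's interaction is left out unless every level has more than 5 events in both arms. If the global test is not significant, the effect is taken to be consistent across subgroups.

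Only if it is significant does selection follow, at 10% throughout: "the least significant interaction terms are removed one-by-one and any newly significant interactions re-included until a final model is reached". All main effects stay in the model. The section then says of this procedure: "This approach will identify the factors that independently alter the treatment effect and prevent identification of multiple correlated interactions". Surviving interactions go on to a Gail and Simon test for qualitative interaction. No error rate, power, multiplicity caveat or exploratory label is attached to the selection.

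**The concern.** Selection at an unadjusted 10% level over several factors keeps any interaction that looks significant by chance. It is run only on datasets already picked out by a significant global test of the same interactions, so chance interactions are over-represented when it starts. Nothing in the procedure controls how many of the named factors are false, and removing terms one at a time does not ensure that the survivor of an overlapping pair is the right one.

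What is at stake is interpretation. A team following the SAP's sentence could tell readers that a named patient group independently has a different PFS benefit, when the list of named factors is more often wrong than right.

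**Working it through.** **Inputs from the SAP.** About 145 patients at 3:2, 87 PFS events, HR 0.54, 80% power and one-sided 2.5% (section 1.3); 60% maturity (section 4.2); eleven factors, the more-than-5-events rule, and 10% for both the global test and the selection (section 4.2.2.2).

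**Assumed, because the SAP gives no values.** Binary prevalences of 10% to 80%; latent correlations of 0.1 to 0.5; the two chemotherapy factors strongly related; either no interaction or one, with a ratio of HRs of 2 or 3.

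**1. The design reproduces.** Events = (1.960 + 0.842)² / (0.6 × 0.4 × (ln 0.54)²) = 7.849 / 0.0911 = 86.1, rounded up to 87; power at 87 is 80.4%. Maturity = 87/145 = 60%.

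**2. Simple bound.** With k independent null interactions each tested at 10%, the chance of at least one false positive is 1 − 0.9^k: 47% for 6 factors, 61% for 9, 69% for 11.

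**3. Power for one true interaction.** z = ln(ratio) × √(87 × 0.24 × q(1 − q)) − 1.645, with q the assumed share of events in one level. For q between 0.3 and 0.5, power is 42% to 48% at ratio 2 and 74% to 81% at ratio 3.

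**4. Simulation of the procedure.** Each trial has 145 patients, 87 events, all main effects, a likelihood-ratio global test at 10%, the event rule, and backward selection at 10% with re-inclusion. There were 1,000 trials per setting (500 where correlation is 0.5). *As written* keeps the SAP's levels, leaving about 6.5 testable factors; *merged* pools rare levels, leaving about 9.

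| Setting | Global test significant | Given that: ≥1 spurious | Given that: true factor named | Given that: exactly the true factor | All trials: ≥1 spurious |
|---|---|---|---|---|---|
| No interaction, as written | 19.3% | 100% | – | – | 19.3% |
| No interaction, merged | 22.2% | 100% | – | – | 22.2% |
| ECOG, ratio 2, as written | 32.8% | 81.1% | 67.7% | 18.9% | 26.6% |
| Best response, ratio 2, as written | 35.4% | 80.5% | 74.9% | 19.5% | 28.5% |
| ECOG, ratio 3, as written | 58.1% | 68.5% | 91.4% | 31.5% | 39.8% |
| ECOG, ratio 3, as written, correlation 0.5 | 54.2% | 70.1% | 84.5% | 29.9% | 38.0% |
| ECOG, ratio 2, merged | 30.9% | 90.6% | 72.5% | 9.4% | 28.0% |
| ECOG, ratio 2, merged, correlation 0.5 | 36.2% | 94.5% | 63.5% | 5.5% | 34.2% |
| ECOG, ratio 3, merged | 57.1% | 82.0% | 90.5% | 18.0% | 46.8% |
| Previous chemotherapy, ratio 3, merged | 56.6% | 86.4% | 74.6% | 13.6% | 48.9% |

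The last column is the first two multiplied, for example 0.328 × 0.811 = 0.266. With no interaction, the mean number of factors named after a significant global test was 2.1 (as written) and 2.9 (merged). Monte Carlo error is small: for the ECOG ratio-2 row, √(0.811 × 0.189 / 328) = 2.2 percentage points.

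Other assumed prevalences gave similar results. One simulation had a spurious factor in 74% (ratio 2) and 69% (ratio 2.5) given a significant global test, and exactly the true factor in 25% and 31%. Another gave 82% to 93% spurious given a significant global test, and about 18% to 43% over all trials.

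**5. The overlapping chemotherapy pair.** Merged levels, true effect in previous chemotherapy, 700 trials per ratio, given a significant global test: both factors named in 16% (ratio 2) and 13% (ratio 3); the type of chemotherapy named instead of the true factor in 21% and 18%. With levels as written the two were never named together, because the event rule mostly removes them.

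**6. Ten times the size** (1,450 patients, 870 events, merged, 250 trials per setting). With no interaction the global test is significant in 10.8%. With a true ratio of 2 the true factor is named in over 99% of trials with a significant global test, yet a spurious factor is still named in 66%.

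**The case against.** Several stronger readings are tempting, and the documents do not support them.

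- *The trial will usually name a spurious factor.* Selection runs only after a significant global test. Over all trials at this size, spurious naming stays under half in every setting tried. The 100% with no interaction is close to circular, since it conditions on a false-positive global test; that test also passes about twice as often as its nominal 10%, which is a separate matter.
- *The procedure does neither thing it promises.* Given a significant global test, a large true interaction is named in most runs, and both members of the chemotherapy pair are seldom kept. The accurate statement is that neither property is guaranteed.
- *It usually names more than one spurious factor.* Not when a true interaction exists. One simulation found two or more null factors in 44%, 36% and 29% of runs at ratios of 2, 2.5 and 3.
- *The trial is simply too small.* Size is only part of the cause, as step 6 shows.
- *Single-factor tests with a Holm correction should replace the selection.* At ratio 2, given a significant global test, Holm cuts spurious naming from 74% to 20% and raises exact naming from 25% to 41%, but detection of the true factor falls from 79% to 47%. It also handles overlap worse: with latent correlation 0.8 it named both correlated factors in 21% against 9.5% (ratio 3) and 16.5% against 11.7% (ratio 2.5). For a consistency screen this is a matter of preference.

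It can also fairly be said that the SAP calls the step an attempt, shows every estimable subgroup HR with its interval, and nowhere orders that retained factors be reported as established modifiers. The interaction test is not repeated for OS (section 4.2.3). All of this limits the consequence. It does not make the quoted sentence true.

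**Conclusion.** The sentence is wrong as written. When the selection is run, its list contains at least one null factor in roughly 70% to 95% of cases with one true two- to three-fold interaction and is exactly right in about 6% to 32%; with no interaction, everything it names is false. The main cause is the unadjusted 10% level across many factors, and small size adds low power. The direction is secure: step 2 needs no assumption about prevalence, and the pattern holds in every setting tried. The exact percentages depend on prevalences, correlations and interaction sizes that the SAP does not state. The clause on correlated interactions fails where both overlapping factors can be tested, which depends on how rare levels are handled.

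The effect is confined to how subgroup consistency for PFS is interpreted. The primary PFS test, the OS test and the type I error control in section 4.2.1 are untouched. Severity: minor.

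**What to change.** In section 4.2.2.2, delete the quoted sentence and put in its place, for example: *The selection is exploratory. No error rate is controlled over the factors it names, and retained factors are often spurious. It will not be concluded from it that a named factor independently alters the treatment effect.*

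Beside the selection, show for each factor with a testable interaction the ratio of HRs with 95% CI and a multiplicity-adjusted interaction p-value (for example Holm across those factors), taken from the single-factor Cox models already planned in the same section. Call this a supportive display and not a replacement. Note under it that single-factor models do not separate overlapping factors such as previous chemotherapy and its type.

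The cost is a few lines of SAP text and one added display; no new model is needed. This version of the SAP is dated 31 January 2020, after the 15 January 2019 cut-off and unblinding, so the added display should be marked post hoc. That timing is a further reason to leave the selection in place and correct only what is claimed for it.

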4.2.3 Overall Survival

A summary of survival status at the time of analysis will be produced. This will summarise the number of patients who have died, who are still in survival follow-up, who are lost to follow-up or who have withdrawn consent. Results will be presented by treatment group.

Interim OS data as defined in Section 3.2.2 will be analysed at the time of the final analysis for PFS (DCO1) and will use the same methodology and model (provided there are sufficient events available for a meaningful analysis [> 5 deaths in both treatment groups], if not descriptive summaries only will be provided). A final formal analysis of OS will be performed when approximately 106 deaths have occurred (DCO2). CCI

Median OS time and corresponding 95% CI will be summarised including the number of deaths, and survival at month 6, 12, 18, 24, 36 and 48. Further timepoints will be added as appropriate. Results will be presented by treatment group.

The analysis will be repeated excluding any patients who did not have a gBRCA mutation status confirmed by the central Myriad test.

The sensitivity analyses outlined for PFS in Section 4.2.2 will not be repeated for OS with the exception of a KM plot. Two KM plots will be produced. The first KM plot will show time to censoring of OS and the second KM plot will show time to censoring where the censoring indicator is reversed (median time to follow-up where events will be censored and previously censored patients will be treated as events). The first KM plot will be repeated excluding any patients who did not have a gBRCA mutation status confirmed by the central Myriad test.

OS data will be listed in a by-patient listing.

Similar subgroup analyses (except the interaction test) will be conducted comparing OS between treatments as detailed for PFS in Section 4.2.2.2, using the same methodology and model. KM plots will be produced for each subgroup according to treatment group. If there are too few events available for a meaningful analysis of a particular subgroup (it is not considered appropriate to present analyses where there are less than 5 events in a subgroup in at least one treatment group), the relationship between that subgroup and OS will not be formally analysed. In this case, only descriptive summaries (number of patients, number (%) of events, and KM plots) will be provided.

4.2.4 Time from randomisation to second progression

The status of PFS2 as defined in Section 3.2.3 will be summarised by the number and percentage of patients experiencing a PFS2 event and the type of progression (objective progression by RECIST, symptomatic progression or death). Results will be presented by treatment group.

The analysis of PFS2 will use the same methodology and model as the primary analysis of PFS. No multiplicity adjustment will be applied as this is viewed as a supportive endpoint.

A KM plot of PFS2 will be provided by treatment group. A KM plot of the time to censoring where the censoring indicator of the PFS2 analysis is reversed will be produced (called median time to follow-up where events will be censored and previously censored patients will be treated as events).

As a key sensitivity, the analysis of PFS2 will be repeated in those patients whose gBRCAm status is confirmed by the Myriad test. A KM plot of PFS2 in this subset of patients will be presented by treatment group.

The median and 95%-CI of PFS2 and the proportion of patients with no second progression at 6, 12, 18, 24, 36 and 48 months will be summarised and presented by treatment group. Further timepoints will be added as appropriate.

Days between second progression and last assessment prior to second progression will be summarised descriptively by treatment group.

A by-patient listing will be produced including details about time of second progression.

4.2.5 Time to first subsequent therapy or death

The TFST will be analysed using the same methodology and model as the primary analysis of PFS. The HRs for the treatment effect together with 95% CIs will be presented. A KM plot will be presented by treatment group, together with status, median TFST and 95% CI for each treatment group.

As a key sensitivity, the analyses of TFST will be repeated in those patients whose gBRCAm status is confirmed by the Myriad test. In this subset of patients, median TFST and 95% CI will be reported by treatment group. In addition, a KM plot of TFST will be presented by treatment group.

The time between progression and starting subsequent cancer therapy will be summarised.

In addition, best overall RECIST response to first subsequent cancer therapy by treatment group will be provided.

Individual TFST will be presented in a by-patient listing.

4.2.6 Time to second subsequent therapy or death

The TSST will be analysed using the same methodology and model as the primary analysis of PFS. The HRs for the treatment effect together with 95% CIs will be presented. A KM plot will be presented by treatment group, together with status, median TSST and 95% CI for each treatment group.

As a key sensitivity, the analyses of TSST will be repeated in those patients whose gBRCAm status is confirmed by the Myriad test. In this subset of patients, median TSST and 95% CI will be reported by treatment group. In addition, a KM plot of TSST will be presented by treatment group.

In addition, best overall RECIST response to second subsequent cancer therapy by treatment group will be provided.

Individual TSST will be presented in a by-patient listing.

4.2.7 Time to study treatment discontinuation or death

The TDT will be analysed using the same methodology and model as the primary analysis of PFS. The HR for the treatment effect together with 95% CIs will be presented. A KM plot will be presented by treatment group, together with status, median TDT and 95% CI for each treatment group.

As sensitivity, the analyses of TDT will be repeated in those patients whose gBRCAm status is confirmed by the Myriad test. In this subset of patients, median TDT and 95% CI will be reported by treatment group. In addition, a KM plot of TDT will be presented by treatment group.

Individual TDT will be presented in a by-patient listing.

